13.8. Future Evaluation of Explanted Units

Evaluation of the explanted units is previously described. However, evaluated units will not be discarded, and there is the possibility of other future evaluations.

14. DATA HANDLING AND RECORD KEEPING

14.1. Data Management Responsibilities

As used in this protocol, the term CRF should be understood to refer to either a paper form or an electronic data record or both, depending on the data collection method used in this study. A CRF is required and should be completed for each included subject. The completed original CRFs are the sole property of the Sponsor and should not be made available in any form to third parties, except for authorized representatives of the Sponsor or appropriate regulatory authorities, without written permission from the Sponsor.

14.2. Data Capture Methods

The Investigator shall capture data in the form and manner required by the Sponsor. The Investigator has ultimate responsibility for the collection and reporting of all clinical and safety data entered on the CRFs and any other data collection forms (e.g., source documents) and ensuring that they are accurate, authentic, original, attributable, complete, consistent, legible, timely (contemporaneous), enduring, and available when required. The Investigator or appropriate site personnel must sign (electronically or hard copy) the CRF(s) to attest that the data contained on the CRFs are true. Any corrections to entries made in the CRFs or source documents must be completed using Good Documentation Practices.

14.3. Types of Data

In most cases, the source documents (the first recording of the data) include, but are not limited to, the hospital's or the physician's subject chart, laboratory reports, etc. The data collected on the CRFs must match the source data. There may be cases where the CRF, or part of the CRF, may

serve as a source document. In these cases, a document should be available at the Investigator's site as well as at the Sponsor and clearly identify those data that will be recorded in the CRF, and for which the CRF will stand as the source document.

It is expected that laboratory data as applicable for each cohort (e.g., safety labs, MMTT, CGM blood glucose data, chemistry, ultrasound results), traceable to a particular subject, will be transmitted electronically to the study database in an ongoing manner during the study.

14.4. Study Records Retention

To enable evaluations and/or audits from regulatory authorities or the Sponsor and its designees, the Investigator agrees to keep records, including the identity of all participating subjects (sufficient information to link records, e.g., CRFs and hospital records), all original signed informed consent documents, copies of all CRFs, safety reporting forms, source documents, and detailed records of treatment disposition, and adequate documentation of relevant correspondence (e.g., letters, e-mails, meeting minutes, telephone calls, reports). The records should be retained by the Investigator according to International Conference on Harmonisation (ICH) local regulations, or as specified in the Clinical Trial Agreement (CTA), whichever is longer.

If the Investigator becomes unable for any reason to continue to retain study records for the required period (e.g., retirement, relocation), the Sponsor should be prospectively notified. The study records must be transferred to a designee acceptable to the Sponsor, such as another Investigator, another institution, or to an independent third party arranged by the Sponsor.

The Investigator must obtain the Sponsor's written permission before disposing of any records.

14.5. Protocol Deviations

Every attempt to follow the protocol as written must be made. However, it is expected there may be deviations resulting from circumstances beyond control or unintentional oversights or mistakes. Any instance of a protocol-required test not being performed at the required time, or within the protocol-described time window, will constitute a protocol deviation. These deviations will be documented by the Investigator or generated systematically and reviewed by the Sponsor. Corrective actions will be put into place to prevent future occurrences of deviations, if possible. These deviations from the protocol must be documented at the site, and the Sponsor must be notified. Depending on the particular EC used at each site, notification of the EC may be warranted as well.

15. DATA PROTECTION

The subject's protected healthcare information shall be treated in compliance with all applicable laws and regulations. When archiving or processing the protected healthcare information of the subjects, the Institution, Investigator, Sponsor and designees shall take all appropriate measures to safeguard and prevent access to these data by any unauthorized third party.

# Statistical Analysis Plan

# ViaCyte, Inc.

Q	Schedule of Assessments	26
	7.3.8 Cohort 2 Exploratory Analyses	24
	7.3.7.3 Cohort 2 Secondary Efficacy Analyses	23
	7.3.7.2 Cohort 2 Secondary Safety Analyses	23
	7.3.7.1 Cohort 1 Secondary Analyses	21
	7.3.7 Secondary Analyses	21
	7.3.6 Primary Analysis	20
	7.3.5 Prior and Concomitant Medications and Procedures	20

#### **Abbreviations** 1

**AE** Adverse Event

ANCOVA Analysis of Covariance Area Under the Curve AUC Body Mass Index BMI

Continuous Glucose Monitoring CGM **DSMB** Data Safety Monitoring Board

Electrocardiogram ECG

**EDDS** Encaptra Drug Delivery System Estimated Glomerular Filtration Rate eGFR

Early Termination ET FAS Full Analysis Set

**FSH** Follicular Stimulating Hormone

Hemoglobin A1C HbA1C

Hepatitis B Surface Antigen HBsAg

Hepatitis C Virus **HCV** Hypoglycemic Event HE

Human Embryonic Stem Cells **hESC** Human Immunodeficiency Virus HIV Human Leukocyte Antigen HLA Informed Consent Discussion ICD

Least Squares Mean LSM

Medical Dictionary for Regulatory Activities MedDRA

Mixed Meal Tolerance Test **MMTT** PEC-01 Pancreatic Endoderm Cells Panel Reactive Antibody PRA

PT Preferred Term

SAE Serious Adverse Event SAP Statistical Analysis Plan SAS Safety Analysis Set

Standard Error SE

SHE Severe Hypoglycemic Event Self-Monitoring Blood Glucose **SMBG** 

System Organ Class SOC

Simplified Oral Glucose Challenge Test **SOGCT** 

Type 1 Diabetes Mellitus T1DM

**Tuberculosis** TB

TEAE Treatment-Emergent Adverse Event VC-01TM Combination Product VC-01 VC-01-DF VC-01 Dose-Finding Unit

#### 2 Introduction

The purpose of this statistical analysis plan (SAP) is to describe in detail the procedures and statistical methods required for completing the final analysis of data in accordance with Protocol VC01-103: *An Open-Label, Phase 1/2 Study to Evaluate the Safety, Engraftment and Efficacy of VC-01*TM *Combination Product in Subjects with Type 1 Diabetes Mellitus (T1DM).* 

Any text in this SAP that comes directly from the Protocol is shown in *italic* font.

## 3 Study Overview

## 3.1 Study Population

Subjects with T1DM will be enrolled into this clinical trial.

## 3.2 Study Design

This will be an open-label clinical trial in subjects with T1DM. Two cohorts are planned for enrollment in this trial.

VC-01 combination product is comprised of two components: (1) PEC-01 pancreatic endoderm cells derived from human embryonic stem cells (hESC) and (2) a durable, cell-impermeable, removable, macroencapsulation device known as the Encaptra drug delivery system (EDDS). Throughout this study, a series of EDDS configurations may be assessed to improve engraftment and cell survival outcomes. It is anticipated that more than one version of the EDDS will be used in this study; hence the term "EDDS configuration" represents a unique version of the EDDS.

Subjects may be implanted with VC-01-DF combination product (for dose-finding) and smaller sentinel combination product. VC-01-ST and VC-01-20 are different configurations of sentinels. The term "sentinel" encompasses both of these smaller units unless specified. These are smaller units that will be explanted at various time points and examined histologically ex vivo.

## Cohort 1– Safety and Engraftment

Up to 30 subjects may be enrolled and receive subcutaneous implantation of up to ten (10) sentinel units. The sentinel units may be explanted at varying time points postimplant to assess graft cell viability, differentiation, vascularization, and host response.

Total duration of treatment may be up to six (6) months for each Cohort 1 subject, with the last unit explanted at Month 6 /Week 26 or earlier if requested by the Sponsor. Cohort 1 subjects will complete a total of up to 12 study visits.

After a minimum of three (3) subjects have been enrolled in Cohort 1 and have completed through Week 4, the Sponsor then has the ability to initiate enrollment of Cohort 2 and

request the DSMB to review the completed Cohort 1 data for safety, tolerability, and proof of mechanism.

## Cohort 2 – Safety and Efficacy

*Up to 40 subjects may be enrolled and receive subcutaneous implantation of:* 

- *Up to nine (9) VC-01-DF units, or;*
- Up to 12 units total. Of the 12 units, no more than nine (9) will be VC-01-DF and the remainder will be sentinel units. For example, if seven (7) VC-01-DF units are implanted in a subject, up to five (5) sentinels may be implanted.

The sentinel units may be explanted at varying time points post-implant to assess graft cell viability, differentiation, vascularization, and host response. At the discretion of the Sponsor and after consultation with the Investigator, explantation of up to two (2) VC-01-DF units is allowed at any time post-implant without needing to withdraw the subject from the study.

Total duration of treatment may be up to one (1) year for each Cohort 2 subject, with the last unit explanted at Month 12/Week 52 or earlier if requested by the Sponsor. Cohort 2 subjects will complete a total of up to 14 study visits.

## 3.3 Study Assessments

Visits will include assessments such as physical examinations (complete, abbreviated, or targeted), 12-lead ECGs, vital signs (sitting blood pressure, pulse rate and temperature) and body weight, ultrasound monitoring, laboratory evaluations, and adverse event collection. Histological assessment of the units will be performed by ViaCyte or a designee, after explantation. Histological assessment of the units may include but is not limited to:

- Survival of implanted cells via cell nuclei count through hematoxylin and eosin staining.
- Differentiation of PEC-01 to endocrine cells (e.g.,  $\alpha$ -cells,  $\beta$ -cells, and/or  $\delta$ -cells) via immunohistochemical staining.
- The host tissue inflammatory or immunological response in the tissue capsule.

Blood glucose monitoring is performed through various methods throughout Cohort 2 of this study to ensure proper glucose control. Investigators will review the blood glucose data at each study visit.

## 3.4 Anticipated Number of Subjects

Total enrollment will be up to 70 subjects. Up to 30 subjects in Cohort 1 and up to 40 subjects in Cohort 2 may be enrolled under this study at approximately ten (10) clinical sites.

## 4 Study Objectives and Endpoints

#### 4.1 Objectives:

Cohort 1 Study Objectives

## Primary Objective:

• Assess via histology the potential for functional engraftment of VC-01 combination product when implanted into subjects with T1DM.

## Secondary Objectives:

- Assess via histology the host immune response to VC-01 combination product when implanted into subjects with T1DM.
- Evaluate the safety and tolerability of VC-01 from implantation to Month 6/Week 26 or earlier if requested by the Sponsor.

## Cohort 2 Study Objectives

## Primary Objective:

• Evaluate the clinical efficacy of VC-01 combination product from implantation to Month 12/Week 52 or earlier if requested by the Sponsor.

## Secondary Objectives:

• Further assess safety and tolerability of VC-01 combination product from implantation to Month 12/Week 52 or earlier if requested by the Sponsor.

## Exploratory Objectives:

- Further assess via histology the potential for functional engraftment of VC-01 combination product when implanted into subjects with T1DM.
- Explore effects of weight, gender, BMI, or other potentially interacting factors on the responsiveness of the subjects to the experimental intervention.
- Optimize the recommended surgical implantation procedure, anatomical location, and peri- and post-operative care for VC-01.
- Further assess the effects of the host immune response to implanted VC-01 units.

## 4.2 Endpoints:

The study endpoints for each Cohort are as follows:

#### Cohort 1 Study Endpoints

## **Primary Endpoints:**

- The percentage of viable graft cells at post-implant time points relative to pre-clinical models.
- The percentage of graft cells staining positive for markers of beta cells at postimplant time points relative to pre-clinical models.

#### Secondary Endpoints:

- The qualitative assessment of the severity of the host immune response as rated at post-implant time points.
- The comprehensive safety profile of VC-01 implanted for up to six (6) months as measured by:
  - *All reported adverse events (AEs).*
  - The incidence of subjects requiring a premature explant due to safety issues.

- The incidence of off-target growth as evidenced by implanted VC-01 units via lumen ultrasound measurements (lumen thickness > 1 mm), or by histological examination of explants.
- The confirmed incidence of immune sensitization defined by presence of donor anti-HLA (human leukocyte antigen) antibodies absent prior to implant in conjunction with either confirmatory histological observations from at least one explanted unit and/or the presence of clinical symptoms. Once sensitization has been confirmed by ViaCyte, an AE of 'sensitization' will be entered into the clinical study database.

## Cohort 2 Study Endpoints

## Primary Endpoint:

• Change from baseline to Week 26 in C-peptide AUC0-4h following a mixed meal tolerance test (MMTT).

## Secondary Endpoints:

Safety and Tolerability

- Comprehensive profile of VC-01 combination product implanted for up to Month 12/Week 52 as measured by:
  - All reported AEs.
  - The incidence of off-target growth as evidenced by implanted VC-01 units via lumen ultrasound (lumen thickness > 1 mm) measurements, or by histological examination of explants.
  - The confirmed incidence of immune sensitization defined by presence of donor anti-HLA antibodies absent prior to implant in conjunction with either confirmatory histological observations from at least one explanted unit and/or the presence of clinical symptoms.
  - Implant tolerability assessments (e.g., fever, erythema, pain, tenderness, induration) post-implantation and at subsequent visits.
  - The incidence of subjects requiring a premature explant due to safety, tolerability, or malfunction issues.

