2.2.1. Cohort 1 Study Endpoints

Primary Endpoint Measures:

- The percentage of viable graft cells at post-implant time points relative to pre-clinical models.
- The percentage of graft cells staining positive for markers of beta cells at post-implant time points relative to pre-clinical models.

Secondary Endpoint Measures:

- The qualitative assessment of the severity of the host immune response as rated at post-implant time points.
- The comprehensive safety profile of VC-01 implanted for up to six (6) months as measured by:
 - All reported AEs.
 - The incidence of subjects requiring a premature explant due to safety issues.
 - The incidence of off-target growth as evidenced by implanted VC-01 units via lumen ultrasound measurements, or by histological examination of explants.
 - The incidence of immune sensitization defined by presence of donor anti-HLA (human leukocyte antigen) antibodies absent prior to implant.

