2.2.2. Cohort 2 Study Endpoints

Primary Endpoint Measure:

• Change from baseline to Week 26 in C-peptide AUC_{0-4h} following a MMTT.

Secondary Endpoint Measures:

Safety and Tolerability

- Comprehensive profile of VC-01 combination product implanted for up to Month 12/Week 52 as measured by:
 - All reported AEs.
 - The incidence of immune sensitization defined by presence of donor anti-HLA antibodies absent prior to implant
 - Implant tolerability assessments (e.g., fever, erythema, pain, tenderness, induration) post-implantation and at subsequent visits.
 - The incidence of subjects requiring a premature explant due to safety, tolerability, or malfunction issues.

Efficacy

- Change from baseline to Weeks 8, 12, 16, 20, 39, and 52 in C-peptide AUC_{0-2h} and change from baseline to Week 52 in C-peptide AUC_{0-4h} following an MMTT.
- Change from baseline to Weeks 16, 20, 26, 39 and 52 in average daily insulin dose in the 7 days preceding the clinic visit.
- Time to onset of biological response of C-peptide following MMTT.
- Percent of subjects achieving a positive stimulated C-peptide (defined as > 0.2 ng/mL) after implant.
- Percent of subjects who achieve a 50% reduction in average weekly exogenous insulin dose from baseline to Weeks 16, 20, 26, 39, and 52.
- Percent of subjects who achieve exogenous insulin independence; of those subjects achieving insulin independence, the percent achieving HbA1c <7.0%.
- Percent of time spent with blood glucose values at various cut points (e.g., <54 mg/dL, ≥54 to <70 mg/dL, ≥70 mg/dL to ≤180 mg/dL, >180 mg/dL and >250 mg/dL) as measured by each subject's CGM.
- Change from baseline to Weeks 16, 20, 26, 39 and 52 in time in euglycemic range (≥70 mg/dL to ≤180 mg/dL), time-in-hypoglycemic ranges (<54 mg/dL and ≥54 to <70 mg/dL), and time-in-hyperglycemic ranges (>180 mg/dL and >250 mg/dL) as measured by each subject's CGM.

Exploratory

• Histological results of explanted units and any associated tissue capsule as evaluated for cell viability, vascularization, immune response, and/or cell maturation and differentiation.

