8.1. Adverse Events

An adverse event (AE) is any untoward medical occurrence in a clinical investigation subject administered a product or medical device. Adverse events need not necessarily have a causal relationship with the treatment or usage.

Examples of AEs include, but are not limited to:

- Abnormal test findings;
- Clinically significant symptoms and signs (changes from baseline status);
- Clinically significant changes in physical examination findings;
- Hypersensitivity;
- Sensitization to the line;
- Progression/worsening of underlying disease (includes worsening diabetes)

All observed or volunteered AEs regardless of suspected causal relationship to the investigational product will be reported as described in the following sections. Non-clinically significant physical exam observations will not be reported as an AE.

For all AEs, the Investigator must pursue and obtain information adequate both to determine the outcome of the AE and to assess whether it meets the criteria for classification as a serious adverse event (SAE) requiring immediate notification to the Sponsor and the Ethics Committee. For all AEs, sufficient information should be obtained by the Investigator to determine the causality of the AE. The Investigator is required to assess causality. Follow-up by the Investigator may be required until the event or its sequelae resolve or stabilize at a level acceptable to the Investigator, and the Sponsor concurs with that assessment.

As part of ongoing safety reviews conducted by the Sponsor, any non-serious AE that is determined by the Sponsor to be serious will be reported by the Sponsor as a SAE. To assist in the determination of case seriousness, further information may be requested from the Investigator to provide clarity and understanding of the event in the context of the clinical trial.

As required on the AE CRFs, the Investigator will use the National Cancer Institute Common Terminology Criteria for Adverse Event (NCI-CTCAE) guidelines to describe the maximum intensity of the AE. For purposes of consistency, these intensity grades are defined as follows:

| MILD | Asymptomatic, or mild symptoms, clinical or diagnostic observations noted; intervention not indicated |
|------------------|---|
| MODERATE | Local or noninvasive intervention indicated |
| SEVERE | Medically significant but not immediately life threatening, hospitalization or prolonged hospitalization. |

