8.1.2. Expected Adverse Reactions

Refer to **Section 1.4.2.1**.

8.1.3. Determination of Abnormal Laboratory Test Values or Abnormal Clinical Findings as Adverse Event

The criteria for determining whether an abnormal, objective test finding should be reported as an AE are as follows:

- Test result is associated with accompanying symptoms, and/or
- Test result is not associated with a known, pre-existing condition or part of the subject's medical history, and/or
- Test result requires additional diagnostic testing or medical/surgical intervention, and/or
- Test result leads to discontinuation from the study, significant additional concomitant drug treatment, or other therapy, and/or
- Test result is considered to be an AE by the Investigator or sponsor.

Merely repeating an abnormal test, in the absence of any of the above conditions, does not constitute an AE. An abnormal test result determined to be an error does not require reporting as an AE.

Evidence of product sensitization (the presence of any donor anti-HLA antibodies absent prior to implant) is not, in itself, considered an AE. The above criteria should also be utilized to determine if the sensitization qualifies as an AE.

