10. STATISTICAL CONSIDERATIONS

Methodology for the summarization and analysis of the data collected in this trial are given here and further detailed in a Statistical Analysis Plan (SAP), which will be maintained by the Sponsor. If the DSMB is requested to review the data from Cohort 1, the study SAP will be written and approved prior to the Cohort 1 data cut-off (e.g., the data through Week 4 for the final subject in Cohort 1 whose data is part of the DSMB data review).

The study SAP may modify what is outlined in the protocol; however, any major modifications of the endpoints or their analyses will be reflected in a protocol amendment.

The phrase "treatment group" is used in this section to denote the number of initially implanted sentinel units in Cohort 1 or initially implanted VC-01-DF dose-finding units in Cohort 2. In Cohort 1, if a subject has a sentinel unit explanted for any reason and remains in the study, then he/she will be included in the treatment group that is described by the number of sentinel units originally implanted. For Cohort 2, if a subject has a VC-01-DF unit explanted for any reason and remains in the study, then she/he will be included in the treatment group that is described by the number of VC-01-DF units originally implanted. If a Cohort 2 subject has no VC-01-DF units implanted, but has sentinel units implanted, then the subject will be included in the "0 implanted VC-01-DF units" treatment group for Cohort 2. If, during the course of the study, further enumeration is needed to differentiate treatment group (for example, if it is necessary to differentiate multiple EDDS configurations used in Cohort 1), then that further detail will be included in the study SAP.

Where appropriate, data from subjects in Cohort 1 and in Cohort 2 will be summarized together (within the same table). When data from the two cohorts is included in the same table, the treatment group will be used to differentiate the data from Cohort 1 and Cohort 2.

[figure not shown]

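### The SAP narrows the protocol's antibody-only immune sensitization endpoint to confirmed cases, and commits no n/N for the incidence the protocol defines

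*SAP*

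**What the plan says.** **Protocol, endpoint definition.** Section 2.2.2 (Cohort 2) reads: "The incidence of immune sensitization defined by presence of donor anti-HLA antibodies absent prior to implant". Section 2.2.1 (Cohort 1) opens the same way, "The incidence of immune sensitization defined by presence of donor anti-HLA", and completes the definition in the same terms. The Protocol Summary repeats it for both cohorts. No further condition is attached.

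**Protocol, adverse events.** Section 8.1.3 uses the same antibody-only meaning: "Evidence of product sensitization (the presence of any donor anti-HLA antibodies absent prior to implant) is not, in itself, considered an AE". It then sends each case to the general criteria for abnormal test results: "The above criteria should also be utilized to determine if the sensitization qualifies as an AE". Section 8.1 includes "Sensitization to the line" among its examples of adverse events.

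**SAP, endpoint definition.** Section 4.2 changes the endpoint in both cohorts to a confirmed incidence. The new antibodies must now occur "in conjunction with either confirmatory histological observations from at least one explanted unit and/or the presence of clinical symptoms". The Cohort 1 text adds a sentence beginning "Once sensitization has been confirmed by ViaCyte, an AE of", which provides for a sensitization event to be entered in the database.

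**SAP, outputs.** Sections 7.3.7.1 and 7.3.7.2 call a subject with new donor antibodies a suspected event. They commit to a listing of these subjects with a column for confirmed status. Summaries of assay data are optional.

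**Rule for changes.** Protocol section 10 lets the SAP modify what the protocol outlines, but says that "any major modifications of the endpoints or their analyses will be reflected in a protocol amendment".

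**The concern.** The two documents name the same safety endpoint and count different subjects. Adding a condition to a case definition can only keep the incidence the same or lower it, which is the less conservative direction for a safety endpoint.

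The added condition also brings in judgement that the antibody criterion does not need. The SAP does not say which histological findings or symptoms confirm a case, and its Cohort 1 text gives confirmation to the sponsor in an open-label trial.

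The antibody result matters in its own right. Protocol 1.4.2.1 names sensitization as a risk to later islet transplant candidacy. That section does not define the term, but it does not make the risk depend on symptoms or explant histology either. A report that follows the SAP could show no confirmed sensitization while some subjects had new donor antibodies. A reader who wanted the protocol's incidence would have to count the cases, and the subjects tested, from listings.

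**Working it through.** The documents state no sensitization rate, threshold or power for this endpoint, so there is no figure to reproduce. The check is a comparison of definitions, a trace of where each count would appear, and simple arithmetic for scale.

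**1. Definitions**

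| Source | Antibodies required | Histology and/or symptoms also required |
|---|---|---|
| Protocol Summary, 2.2.1, 2.2.2 | Yes | No |
| Protocol 8.1.3 (meaning of the term) | Yes | No |
| SAP 4.2, both cohorts | Yes | Yes |

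Let A be the number of subjects with new donor antibodies and C the number who also have confirmatory histology and/or symptoms. Every subject in C is in A, so C/N ≤ A/N for any common N.

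**2. Where each count would appear**

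- *C (confirmed).* Each confirmed case is assured a sensitization adverse event (SAP 4.2, 7.3.7.1, 7.3.7.2), and so reaches the treatment-emergent summaries. The SAP plans no dedicated incidence table for C.
- *A (protocol definition).* These subjects appear in the suspected-event listing, and SAP section 5 lists all collected data. Unconfirmed cases reach the adverse event tables only if they separately meet the criteria in Protocol 8.1.3. Those tables therefore cannot be relied on to give A.
- *Denominator.* No output commits the number of subjects with a baseline and a post-implant antibody test.

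**3. Size of the gap**

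Gap in percentage points = k/N × 100, where k = A − C. N is the enrolment ceiling in SAP 7.1: 30 in Cohort 1 and 40 in Cohort 2. The value of k is an assumption.

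| k | Cohort 2 (N = 40) | Cohort 1 (N = 30) |
|---|---|---|
| 0 | 0 | 0 |
| 1 | 2.5 | 3.3 |
| 2 | 5.0 | 6.7 |
| 3 | 7.5 | 10.0 |

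If fewer subjects are enrolled or tested, each one shifts the figure by 100/N points, which is more than shown.

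**4. Illustration at the top of that range**

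Assume, for Cohort 2 with N = 40, an antibody incidence of 10% of which 25% is confirmed, with subjects independent.

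- Expected antibody-positive: 40 × 0.10 = 4, or 10.0%.
- Expected confirmed: 40 × 0.10 × 0.25 = 1, or 2.5%. The gap is 3/40 = 7.5 points.
- Chance of at least one antibody-positive subject: 1 − 0.90^40 = 0.985.
- Chance of at least one confirmed subject: 1 − 0.975^40 = 0.637.

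Under these assumed rates, about 36% of such trials would report no confirmed case, while fewer than 2% would have no antibody-positive subject.

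**The case against.** The strongest reply is that this is a permitted and largely transparent refinement.

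- *The SAP may modify the protocol.* This stands. Whether the change counts as major, and so needs an amendment, is a judgement, and no breach of Protocol section 10 is claimed. The SAP also sets protocol text in italics (section 2), so the added words may have been typographically marked as its own. Neither point reconciles the two definitions or supplies the antibody-only incidence.
- *Every antibody-positive subject is listed.* This stands and limits the harm. With at most 40 subjects per cohort, the numerator can be counted. A listing of positives still gives no percentage by treatment group and no number tested, although the endpoint is an incidence.
- *The protocol plans no such table either.* This is true of Protocol 10.4.4.1 and 10.4.4.2.1, so the missing table is not purely the SAP's doing. The narrowed definition is.
- *Unconfirmed cases may become adverse events anyway.* This is possible under Protocol 8.1 and 8.1.3, but it is not assured.
- *Confirmation can usually be attempted.* Remaining units come out at the final visit (Protocol 6.11.1, 6.13) and explanted units go for histology (7.11). The gap is therefore confined to subjects with neither confirmatory histology nor symptoms.
- *Nothing formal depends on it.* No hypotheses are tested, and the stopping rules in Protocol 8.6 do not name antibody incidence. This limits the seriousness of the point but does not answer it.

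**Conclusion.** The concern holds. SAP 4.2 replaces the protocol's case definition for a named secondary safety endpoint in both cohorts, and the supplied protocol does not reflect the change. The antibody-only event is relegated to a listing, with no committed n/N.

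The direction is certain: the SAP incidence is equal to or below the protocol's. The size is not known. It is 2.5 points per unconfirmed antibody-positive subject in Cohort 2 and 3.3 in Cohort 1 at full enrolment. That gives 0 to 7.5 and 0 to 10.0 points for an assumed 0 to 3 such subjects. These figures rest on the enrolment ceilings and on an assumed k, and the actual gap may be zero.

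The sponsor should correct this. Because the cases are listed, it is a definition and reporting fault rather than a loss of safety information.

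**What to change.** In SAP 4.2, 7.3.7.1 and 7.3.7.2:

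1. Restore the antibody-only definition as the endpoint in both cohorts.
2. Commit to one table of n/N (%) by treatment group and overall, with N = subjects who have a baseline and at least one post-implant antibody test.
3. Show the confirmed subset as an additional row, and keep the listing.

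If the sponsor prefers the confirmed definition, it should reconcile the documents by protocol amendment or a stated SAP deviation, and still report the antibody-only row.

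The cost is SAP wording and one extra table. The samples are already scheduled: baseline and Weeks 4, 16 and 26 in both cohorts, plus Week 52 in Cohort 2 (Protocol Tables 1 and 2). Immune-panel results would have to be brought into the analysis database, because Protocol 7.17.3 treats their inclusion there only as a possibility. The one downside for the sponsor is that the reported incidence may be higher.
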